7.7 Visit Windows

The post-transplant weekly visits must occur on the scheduled day \pm 3 days. The 75 day visit must occur at day 75 ± 5 days. Monthly visits must occur \pm 10 days. For example, a subject receiving a transplant on the 15th of one month should have follow-up visits between the 5th and the 25th of subsequent months. All other visits are scheduled on a quarterly basis from the last transplant, and should occur within 14 days (plus or minus) of the calendar date for the transplant. A subsequent transplant resets this schedule. Pre-transplant visit windows would follow the same weekly, monthly, or quarterly post-transplant windows when applicable.

7.8 Study Treatment Assignment Procedures

7.8.1 Blinding and Randomization

This is an open-label, non-randomized study. Therefore, no blinded treatment codes are required for the assignment of study treatment.

8. SAFETY MONITORING

AEs that are classified as serious according to the definition set forth by the health authorities must be reported promptly to University of Iowa DCC, health authorities, PIs, and IRBs. This section defines the types of AEs and outlines the procedures for appropriately collecting, grading, recording, and reporting them. Information in this section complies with *International Conference on Harmonization (ICH) Guideline E2A: Clinical Safety Data Management: Definitions and Standards for Expedited Reporting* and *ICH E6: Guideline for Good Clinical Practice*, and applies the standards set forth in the most current version of the *CIT- TCAE*. This document, created by the Clinical Islet Transplantation (CIT) Consortium, modifies the National Cancer Institute (NCI), *Common Terminology Criteria for Adverse Events (CTCAE) version 4.1 (July 16, 2008)*, to ensure applicability in the setting of Islet Transplantation.

8.1 Definitions

8.1.1 Adverse Event

An AE is any occurrence or worsening of an undesirable or unintended sign, symptom (including an abnormal laboratory finding), or disease that is temporally associated with the use of a medicinal product whether considered related to the medicinal product or not.

8.1.2 Serious Adverse Event

An SAE is defined per 21CFR§312.32 as “any AE occurring at any dose that suggests a significant hazard, contraindication, side effect, or precaution.” This includes but is not limited to any of the following events:

1. Death.
2. A life-threatening event. A life-threatening event is any adverse therapy experience that, in the view of the investigator, places the patient or participant at immediate risk of death from the reaction as it occurred.
3. In-patient hospitalization or prolongation of existing hospitalization. Please note that hospital admissions for the purpose of conducting protocol-mandated procedures do not need to be reported as SAEs, unless the hospitalization is prolonged due to complications.
4. Persistent or significant disability.
5. Congenital anomaly or birth defect.
6. An event that required intervention to prevent permanent impairment or damage. An important medical event that may not result in death, be life-threatening, or require hospitalization may be considered an SAE when, based on appropriate medical judgment, it may jeopardize the subject and may require medical or surgical intervention to prevent one of the outcomes listed in this definition.
7. Other conditions specified in the protocol.

In addition, events that occur at a higher than expected frequency, as determined by appropriate medical judgment, may be considered SAEs.

Regardless of the relatedness of the AE to the investigational agent, the event must be identified as an SAE if it meets any of the above definitions.

8.1.3 Unexpected Adverse Event

An AE is considered “unexpected” when its nature (specificity) or severity is not consistent with available product information provided in the package insert, the protocol, or the investigator’s brochure.

8.2 Adverse Events

8.2.1 Collecting Procedure

Only AEs that are associated with a protocol mandated procedure, which is not part of the normal standard of care for the subject, and severe hypoglycemic events (see study definitions), will be collected after the screening consent has been obtained and until the subject initiates standard diabetes care or is placed on the wait list (whichever comes first). All AEs will be collected from at the time the subject initiates study-directed diabetes care or is placed on the protocol waitlist (whichever comes first) until study completion, or for 30 days after the subject prematurely withdraws from the study. AEs will be followed until the time the event is resolved, stabilized, or the subject completes or withdraws from the study, whichever comes first.

AEs may be discovered through any of these methods:

- Observing the subject.
- Questioning the subject, which should be done in an objective manner.
- Receiving an unsolicited complaint from the subject.
- An abnormal value or result from a clinical or laboratory evaluation (e.g., a radiograph, an ultrasound, or an ECG) can also indicate an AE. If this is the case, then the evaluation that produced the value or result should be repeated until the value or result returns to normal or can be explained and the subject's safety is not at risk. If an abnormal value or result is determined by the investigator to be clinically significant, it must be reported as an AE.

8.2.2 Recording Procedure

Throughout the study, the investigator will record all AEs on the appropriate AE CRF regardless of their severity or relation to study medication or study procedure. The investigator will treat subjects experiencing AEs appropriately and observe them at suitable intervals until their symptoms resolve or their status stabilizes.

8.2.3 Grading and Attribution

GRADING CRITERIA

The study site will grade the severity of AEs experienced by study subjects according to the criteria set forth in the most current version of the *CIT-TCAE*. This document provides a common language to describe levels of severity, to analyze and interpret data, and to articulate the clinical significance of all AEs.

AE severity will be graded on a scale from 1 to 5 according to the following standards in the *CIT-TCAE* manual:

- Grade 1 = Mild AE.
- Grade 2 = Moderate AE.
- Grade 3 = Severe and undesirable AE.
- Grade 4 = Life-threatening or disabling AE.
- Grade 5 = Death.

AEs, not included in the *CIT-TCAE* listing, should be recorded and their severity graded from 1 to 5 according to the General Grade Definition provided below.

Table 5. General Severity Definition of Adverse Event

Grade 1	Mild	Transient or mild discomforts (< 48 hours), no or minimal medical intervention/therapy required, hospitalization not necessary (non-prescription or single-use prescription therapy may be employed to relieve symptoms, e.g., aspirin for simple headache, acetaminophen for post-surgical pain).
Grade 2	Moderate	Mild to moderate limitation in activity some assistance may be needed; no or minimal intervention/therapy required, hospitalization possible.
Grade 3	Severe	Marked limitation in activity, some assistance usually required; medical intervention/therapy required hospitalization possible.
Grade 4	Life-Threatening	Extreme limitation in activity, significant assistance required; significant medical/therapy intervention required hospitalization or hospice care probable.
Grade 5	Death	Death.

All AEs will be reported and graded by the PI or designee whether they are or are not related to disease progression or study treatment.

DEFINITION OF ATTRIBUTION

Attribution will only be determined and collected for serious adverse events.

The relatedness, or attribution, of an AE to islet transplantation, which includes the transplant procedures and/or the islet product, or to the immunosuppression and/or infection prophylaxis will be determined by the site investigator. The site investigator will also record the determination of attribution on the appropriate eCRF and/or SAE report form. The relationship of an AE (attribution of AE) to islet transplantation and/or immunosuppression and/or infection prophylaxis and/or standard diabetes care will be defined by using the descriptors provided below.

Table 6. Attribution of Adverse Events

Code	Descriptor	Definition
UNRELATED CATEGORY		
1	Unrelated	The AE is clearly not related to allogeneic islets; the islet transplant procedure; immunosuppression or infection prophylaxis.
RELATED CATEGORIES		
2	Unlikely	The AE is doubtfully related to allogeneic islets; the islet transplant procedure; immunosuppression or infection prophylaxis.
3	Possible	The AE may be related to allogeneic islets; the islet transplant procedure; immunosuppression or infection prophylaxis.
4	Probable	The AE is likely related to allogeneic islets; the islet transplant procedure; immunosuppression or infection prophylaxis.
5	Definite	The AE is clearly related to allogeneic islets; the islet transplant procedure; immunosuppression or infection prophylaxis.

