4.1 Study Endpoints

Since our primary thesis is that GLASSIA will increase islet engraftment in the early perioperative period our primary endpoint for which the study is powered is a comparison of insulin independence rates of GLASSIA treated versus control patients at day 75 post transplant. We are fortunate to have permission to utilize data from the CIT-06 trial which will allow a large number of control patients. Since our proposed trial was directly derived from CIT-06 in terms of entry criteria, treatment regimen and post transplant monitoring except for treatment with GLASSIA and related mechanistic studies, these cohorts provide us a highly relevant comparator and allow us to enroll more GLASSIA treated patients than if a randomized trial. This increases the power of the trial making it likely that we will be able to detect differences between treated and control groups should GLASSIA exert the hypothesized benefit to engraftment.

For our primary mechanistic assessment to measure engrafted functional islet mass we will rely on the frequently sampled intravenous glucose tolerance test (FSIGT) from which an AUC for insulin secretion correlates with islet mass. Each of the 24 CIT-06 patients had this test performed at day 75. Of note, we had previously considered use of a glucose potentiated arginine stimulation test for this purpose. However, no CIT-06 patients had this test performed¹³¹⁻¹³².

Because the assessment of islet graft function is dependent on complex physiologic relationships between the graft and its recipient, no single test adequately addresses the metabolic impact of the transplant. Therefore, HbA1c and the number of episodes of severe hypoglycemia will be used as clinically relevant measures of islet graft function for secondary endpoints, and additional stimulatory tests of islet graft function utilizing MMTT, glucose, and the CPGCR will be used to assess secondary endpoints. Also, the effect of islet graft function on glycemic control (HbA1c), glycemic lability (MAGE and LI), hypoglycemia (Clarke and HYPO scores), glucose variability (CGMS®), cardiovascular impact, and renal impact will be assessed as additional secondary endpoints¹³²⁻¹³⁶. Each of these were collected in CIT-06 patients and will add to the robustness of our comparison of the metabolic outcome between GLASSIA treated and control CIT-06 subjects.

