5. STUDY TREATMENT REGIMEN

Please refer to Section 1.5 and to applicable package inserts and product labeling for known and potential risks to human subjects associated with the study treatment regimen.

Table 1. Islet Transplant and Immunosuppression Regimen

	Days Relative to Transplant												
	-2	-1	0	1	2	3	4	5	6	7	10	14	21
Islet Transplant			X										
ATG (Initial Transplant Only)	X	X	X	X	X								
Basiliximab (Subsequent Transplants Only)			X				X						
AAT			X										AAT will be given on Monday, Wednesday, Friday schedule for total of 9 doses in 3 weeks
Etanercept			X				X				X	X	

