5.1 Investigational Agent: GLASSIA

GLASSIA is human alpha1 proteinase inhibitor indicated in patients with lung disease secondary to severe hereditary deficiency of alpha1-antitrypsin (AAT). For this purpose the recommended dose for chronic therapy is 30 mg/kg once weekly at a rate of 0.2 ml/kg/min via iv infusion. In the current trial, patients will receive a 90 mg/kg load followed by 30mg/kg 3x/week for 3 weeks. It should take approximately 30 minutes to infuse. Its use is contraindicated in patients with IgA deficiency with anti-IgA antibodies as this may result in severe hypersensitivity and or anaphylaxis. GLASSIA is pregnancy category C.

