5.1.1 Formulation, Dosing, Administration and Emergency Precautions

GLASSIA (Kamada) is available commercially as a ready to use, liquid preparation of purified human-alpha₁-protease inhibitor (Alpha₁-PI). It is prepared from human plasma though cold ethanol fractionation. GLASSIA is available in with UPS Water for Injection (to 1 gm/50ml).

The first dose of GLASSIA will be calculated with the recipients body weight recorded during the admission for transplant. Subsequent doses will be calculated using the weight recorded on the admission for that dosing. The dose will be rounded to the nearest whole vial dose but must be within

10% of calculated dose. Patients will receive a loading dose of 90 mg/kg followed by maintenance dose of 30mg/kg/dose. A trough level will be measured between 2nd and 3rd dose. If the AAT level is not between 2.5-3.5 mg/ml we will increase dose to 60mg/kg/dose for the remaining doses.

GLASSIA will be used within three hours per package insert guidelines. The infusion will be administered by a qualified individual, using a 5 micron in-line filter during the infusion. Vital signs will be recorded within 30 minutes before initiating the infusion and every 30 minutes during the infusion and within 15 minutes after completing the infusion.

With each infusion, medical personnel will be available to treat subjects who experience anaphylaxis. Emergency treatment such as 0.3 mL to 0.5 mL aqueous epinephrine (1:1000 dilution) subcutaneously and other resuscitative measures including oxygen, IV fluids, antihistamines, corticosteroids, pressor amines, and airway management, as clinically indicated, should be provided.

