5.8.3 Premature Discontinuation of Study Treatment (Transition to “Reduced Follow- up” Treatment)

Study treatment will begin at the time of the first dose of induction antibody therapy for an islet transplant. Study treatment may be prematurely discontinued for any subject for any of the following reasons:

- The subject is unwilling or unable to comply with the protocol.
- The investigator believes that the study treatment is no longer in the best interest of the subject.
- The renal allograft is lost and the subject elects to terminate chronic immunosuppression.
- Graft Failure: See Study Definitions and Section 5.8.2.
- An unexpected related SAE. The agent(s) to which the event is attributed will be discontinued.

Subjects who prematurely discontinue study treatment will remain in the study until normal termination, for the purpose of monitoring safety and efficacy parameters and will enter the reduced follow-up schedule outlined in Appendix 2. Data from these subjects will be used in the intent-to-treat analysis.

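### The protocol's only graded SAE attribution scale (Section 8.2.3 and Table 6) omits GLASSIA, so as written it gives no GLASSIA-specific attribution

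*Combined protocol and SAP*

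**What the plan says.** Section 8.2.3 limits the exercise at the outset: "Attribution will only be determined and collected for serious adverse events". Two sentences then list the sources to be judged. The first names islet transplantation (procedure and product), immunosuppression and infection prophylaxis. The second lengthens the list, speaking of "The relationship of an AE (attribution of AE) to islet transplantation and/or immunosuppression and/or infection prophylaxis and/or standard diabetes care", and says that the descriptors in Table 6 define that relationship. Table 6 has one unrelated code and four related codes, running from unlikely to definite. Code 1 reads "The AE is clearly not related to allogeneic islets; the islet transplant procedure; immunosuppression or infection prophylaxis", and codes 2 to 5 use the same four sources.

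Elsewhere the protocol treats GLASSIA as an agent in its own right. Section 5.1 is headed as an investigational agent section. Section 4.1 says the trial derives from CIT-06 in its "treatment regimen and post transplant monitoring except for treatment with GLASSIA and related mechanistic studies". Section 5.1.1 provides for emergencies: "With each infusion, medical personnel will be available to treat subjects who experience anaphylaxis".

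**The concern.** An attribution scale in a trial of a new agent should let the investigator say whether an event is due to that agent. This one does not name it. The trial is open-label and non-randomized (7.8.1). Section 10 plans to tabulate adverse event rates with confidence intervals (10.1.3) but describes no general comparison of adverse events with CIT-06. Investigator attribution is therefore one of the few routes to safety information specific to GLASSIA. At stake are the GLASSIA-related SAE count and consistent coding of the same event across sites.

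**Working it through.** No sample size, error rate or event count is involved, so the check is textual. Every statement on attribution or relatedness was read, to see whether GLASSIA or AAT is named and whether a second scale exists.

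**Count**
- Table 6 definitions naming GLASSIA, AAT, study drug or investigational agent: 0 of 5.
- Sentences in 8.2.3 listing attribution sources that name any of these: 0 of 2.
- Graded attribution scales in the protocol: 1.

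**How an SAE caused by GLASSIA would be coded**
1. *Literal reading, no overlap.* If the investigator judges the four listed sources clearly excluded, code 1 applies and the event is recorded as unrelated. The plainest example is a reaction during a GLASSIA infusion, for which 5.1.1 takes precautions.
2. *Literal reading, with overlap.* Section 1.5.2 gives increased clotting and viral infection as the rare serious reactions to GLASSIA. Clotting overlaps with portal vein thrombosis after islet infusion (1.5.5.10), and viral infection with the infection risk of immunosuppression (1.5.3). Code 1 needs clear exclusion of the listed sources, and even a doubtful relation (code 2) falls in the related group. Such events would usually be coded related, but to the listed sources.
3. *AAT read as immunosuppression.* Table 1, titled "Islet Transplant and Immunosuppression Regimen", has an AAT row. A site taking that view would code the event related, but pooled with ATG, basiliximab, etanercept and maintenance drugs.

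Route 1 gives a wrong code. Routes 2 and 3 give a non-specific one. None yields a GLASSIA-specific attribution, and 8.2.3 does not say which reading applies.

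**Is the third reading the intended one?** The rest of the protocol points away from it. Section 1.4 describes GLASSIA as paired with the standard immunosuppression. Its risks are in 1.5.2, while 1.5.3 names basiliximab, ATG and etanercept. Its treatment section is 5.1, while immunosuppression medications are in 5.3.

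**Where relatedness is used without a scale**
- 5.8.3, after an unexpected related SAE: "The agent(s) to which the event is attributed will be discontinued".
- 6.2.1: relation to the test therapy, as found by the Protocol Chair.
- 8.3.3: whether an SAE is drug related, for reporting to health authorities.

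None of these cites Table 6, and the scale supplies none of them with a GLASSIA judgement from the site.

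**A separate mismatch.** Standard diabetes care is in the second sentence of 8.2.3 but in none of the Table 6 definitions that are said to define it.

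**The case against.** The strongest reply is that the gap is confined to wording and has little practical reach. Much of that stands.

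- *A reader might infer that the protocol provides for no attribution to GLASSIA at all.* It does not say that. Sections 5.8.3, 6.2.1 and 8.3.3 each call for a judgement about an agent, the test therapy or a drug. What is missing is a graded scale that records it.
- *A reader might infer that most GLASSIA reactions would be coded unrelated.* The overlap described above argues otherwise. All subjects are already on maintenance immunosuppression, and code 1 needs clear exclusion. A false unrelated code is mainly a risk for infusion reactions; for other events the loss is of specificity.
- *A reader might take 5.1 as foreseeing anaphylaxis in enrolled subjects.* Its statement that "this may result in severe hypersensitivity and or anaphylaxis" concerns patients with IgA deficiency and anti-IgA antibodies, and exclusion criterion 27 removes selective or severe IgA deficiency. Only the general precaution in 5.1.1 supports the infusion-reaction example.
- *A reader might infer that an expedited report or a suspension would be missed.* Under 8.3.3 every SAE goes to the DCC within 24 hours of discovery and to the sponsor within a further 2 business days, and all SAEs are listed for the DSMB at least yearly. The site suspension rule in 6.2.2 refers to events possibly related to the study, which covers GLASSIA.
- *The eCRF, SAE form and Manual of Procedures are not among the documents.* They may already hold a GLASSIA field. That limits what can be said about practice. It does not cure the protocol text, which defines what the investigator determines and records.

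The reply does not dispose of the omission itself. The Table 1 defence, even if accepted, still leaves GLASSIA indistinguishable from the drugs it is added to.

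**Conclusion.** The point holds as a defect in the scale as written. GLASSIA appears in 0 of 5 codes and 0 of 2 source-listing sentences of the only graded scale, and no available reading gives a GLASSIA-specific SAE attribution. Confidence in the omission is high, because it rests on the text alone. How many SAEs would be affected cannot be estimated: the documents give no expected frequency, and Section 10 plans no analysis by relatedness, so no rate or interval is offered. All-cause SAE rates remain available and the primary endpoint is unaffected. The conclusion assumes that no unseen form or manual supplies the missing item; if one does, the protocol still needs to agree with it. This should be fixed, at the lower end of that category.

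**What to change.** Add GLASSIA (AAT) as a separately scored attribution source in the 8.2.3 text and in Table 6. Make the Table 6 sources match the lead-in sentence, including standard diabetes care. Confirm that the eCRF and SAE report form carry the same sources. Tabulate GLASSIA-related SAEs alongside all-cause SAEs. The relatedness terms in 5.8.3, 6.2.1 and 8.3.3 must be reconciled with the scale; no stopping, suspension or reporting rule needs to change for this purpose.

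The cost is an amendment to one section and one table, plus one safety table. Whether the forms need changing cannot be told from the documents.

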8.3 Serious Adverse Events

8.3.1 Collecting Procedure

SAEs will be collected following the subject's signing of the screening consent to participate in the study until 30 days after the subject completes or withdraws from the study. SAEs will be followed until the time the event is resolved, stabilized, or until 30 days after the subject completes or withdraws from the study, whichever comes first.

8.3.2 Recording Procedure

SAEs will be recorded on the AE eCRF.

